1.4 Rationale for conducting this study

HIV-1-infected patients with cancer have been systematically excluded from clinical trials of anti cancer drugs because of concerns related to drug interactions and the unknown effect of the underlying HIV infection on the safety and activity of the investigational drugs. Anti PD-L1 antibody durvalumab (MEDI4736) could be an active treatment both for cancer and for HIV infection, with non-expected drugs interactions.

1.5 Benefit/risk and ethical assessment

The benefit-risk relationship has been carefully considered in the planning of the trial. Based on the nonclinical and clinical studies available to date, the conduct of the trial is considered justifiable using the dose and dose regimen of the durvalumab as specified in this clinical trial protocol.

The trial shall be discontinued in the event of any new findings that indicate a relevant deterioration of the risk-benefit relationship that would render continuation of the trial unjustifiable.

The primary known risks of exposure to durvalumab include:

- Infusion-related reactions and
- irAEs

In addition, since durvalumab could induce antibody-dependent cell-mediated cytotoxicity (ADCC), there is a potential risk of tumor lysis syndrome.

Clinical trials with antibodies that block PD-1/PD-L1 interaction have been reported to produce objective response rates of 7% to 38% in patients with advanced or metastatic solid tumors, with response duration of 1 year or more for the majority of patients(22-30).

Clinical Study Protocol

Drug Substance Durvalumab (Medi4736)

Sponsor code: GECP 16/04_ [REDACTED]

Version Number 4.1

Date 14th November 2018

Given the suboptimal treatment options for patients with recurrent locally advanced or metastatic solid tumors in HIV-1 infected patients, and the safety profile of durvalumab, the risk-benefit ratio of treatment with durvalumab in the targeted trial population is considered positive.

This clinical trial protocol will be conducted in compliance with the clinical trial protocol, ICH GCP and the applicable national regulatory requirements.

2. STUDY OBJECTIVES

2.1 Primary objective(s)

To explore the feasibility of durvalumab (MEDI4736) monotherapy at the recommended dose of 1500 mg every 4 weeks in solid tumors in HIV-1-infected patients.

HIV-1-infected patients with cancer have been systematically excluded from clinical trials of anti cancer drugs because of concerns related to drug interactions and the unknown effect of the underlying HIV infection on the safety and activity of the investigational drugs. Anti PD-L1 antibody durvalumab (MEDI4736) could be an active treatment both for cancer and for HIV infection, with non-expected drugs interactions. The aim of this study is to explore the feasibility of durvalumab (MEDI4736) in HIV-1-infected patients who are diagnosed with a solid tumor (lung cancer, head and neck cancer, cervical cancer, melanoma, anal cancer, pancreatic cancer, gastroesophageal cancer, triple negative breast cancer, bladder cancer, renal cancer, Cholangiocarcinoma, Kaposi sarcoma, lymphomas, ovarian cancer, Merkel cell carcinoma or any other tumor type in which anti PD-1 or anti PD-L1 antibodies have demonstrated antitumoral activity) for which no additional oncologic standard treatment is available, or for which the subject declines standard treatment.

2.2 Secondary objective(s)

- To assess ORR (RECIST 1.1 and irRECIST) and duration of response

Clinical Study Protocol

Drug Substance Durvalumab (Medi4736)

Sponsor code: GECP 16/04_ [REDACTED]

Version Number 4.1

Date 14th November 2018

- To evaluate the PFS rate at 6 months
- To evaluate the OS rate at 12 months

Durvalumab (MEDI4736) has demonstrated activity in several cancer types in the general population. In this study, as secondary objective, we will analyze activity of the drug as activity in terms of Response rate according to RECIST1.1 criteria, and according to OS rate at 12 months and PFS at 6 months.

Several data indicate that anti PD-1/PD-L1 treatments in oncology could have activity in terms of OS with long responders, that it is not always correlated to classical endpoint of response rate or median survival.

In this trial given that patients will be included with different solid tumors, and different lines of treatment, activity of the drug is a secondary objective, in order to determine if activity looks similar to activity reported in solid tumors without HIV- infection.

Clinical Study Protocol

Drug Substance Durvalumab (Medi4736)

Sponsor code: GECP 16/04_

Version Number 4.1

Date 14th November 2018

Clinical Study Protocol

Drug Substance Durvalumab (Medi4736)

Sponsor code: GECP 16/04_ [REDACTED]

Version Number 4.1

Date 14th November 2018

3. STUDY DESIGN

3.1 Overview of study design

This is a multicenter, national, non-randomized, phase II study in HIV-1 infected patients with advanced solid tumors.

Twenty evaluable patients will be included in the trial. Patients will be included irrespective of number the previous line of treatments.

[figure not shown]
The clinical trial will be performed in 10 hospitals from the Spanish Lung Cancer Group in Spain with a competitive enrollment.

It is a single arm study. All patients included will received the treatment with durvalumab (MEDI4736). There is not placebo treated patients.

Patients must have stopped the previous treatments for cancer at least 30 days before starting study medication.

3.2 Study schema

Figure 1. Study flow chart

Clinical Study Protocol

Drug Substance Durvalumab (Medi4736)

Sponsor code: GECP 16/04_ [REDACTED]

Version Number 4.1

Date 14th November 2018

3.3 Study Oversight for Safety Evaluation

The whole trial may be discontinued prematurely in the event of any of the following situations:

- New information leading to unfavourable risk-benefit judgement of the trial drug, as inefficacy of the drug for this population, significant previously unknown adverse reactions or unfavourable safety findings.
- Sponsor's decision that continuation of the study is unjustifiable for medical or ethical reasons.

4. SUBJECT SELECTION

Only persons meeting the inclusion criteria and no exclusion criteria may be enrolled into the trial. Prior to performing any trial assessments not part of the routine medical care, the investigator will ensure that the subjects have provided written informed consent.

4.1 Inclusion criteria

For inclusion in the study subjects must fulfill all of the following criteria:

1. Written informed consent obtained from the subject prior to performing any protocol-related procedures, including screening evaluations.
2. Age \geq 18 years at time of study entry.
3. Eastern Cooperative Oncology Group (ECOG) 0-2.
4. Life expectancy of \geq 16 weeks.
5. Adequate normal organ and marrow function as defined below:
 - Haemoglobin \geq 9.0 g/dL
 - Absolute neutrophil count (ANC) \geq 1.5 x 10⁹/L (\geq 1500 per mm³)
 - Platelet count \geq 100 x 10⁹/L (\geq 100,000 per mm³)
 - Serum bilirubin \leq 1.5 x institutional upper limit of normal (ULN). This will not apply to subjects with confirmed Gilbert's syndrome (persistent or recurrent

hyperbilirubinemia that is predominantly unconjugated in the absence of hemolysis or hepatic pathology), who will be allowed only in consultation with their physician.

- AST (SGOT)/ALT (SGPT) \leq 2.5 x institutional upper limit of normal unless liver metastases are present, in which case it must be \leq 5x ULN
- Serum creatinine CL > 40 mL/min by the Cockcroft-Gault formula (Cockcroft and Gault 1976) or by 24-hour urine collection for determination of creatinine clearance:

Males:

$$\text{Creatinine CL} = \frac{\text{Weight (kg)} \times (140 - \text{Age})}{72 \times \text{serum creatinine (mg/dL)}}$$

Females:

$$\text{Creatinine CL} = \frac{\text{Weight (kg)} \times (140 - \text{Age}) \times 0.85}{72 \times \text{serum creatinine (mg/dL)}}$$

6. Female subjects must either be of non-reproductive potential (ie, post-menopausal by history: \geq 60 years old and no menses for \geq 1 year without an alternative medical cause; OR history of hysterectomy, OR history of bilateral tubal ligation, OR history of bilateral oophorectomy) or must have a negative serum pregnancy test upon study entry.
7. Subject is willing and able to comply with the protocol for the duration of the study including undergoing treatment and scheduled visits and examinations including follow up.
8. Subjects with histologically or cytologically-documented advanced/metastatic lung cancer, head and neck cancer, cervical cancer, melanoma, anal cancer, pancreatic cancer, gastroesophageal cancer, triple negative breast cancer, bladder cancer, renal cancer, Cholangiocarcinoma, Kaposi sarcoma, lymphomas, ovarian cancer, Merkel cell carcinoma or any other tumor type in which anti PD-1 or anti PD-L1 antibodies have demonstrated antitumoral activity, refractory to standard treatment, intolerant of standard treatment, or for which no standard therapy exists or who refuse the standard treatment.

9. Subjects may be included irrespectively of number of previous lines of treatment for advanced disease.
10. Prior palliative radiotherapy must have been completed at least 2 weeks prior to start the study treatment (subjects may receive localized palliative radiotherapy while receiving study drug).
11. Documented HIV-1 infection
12. Undetectable viral load in the last analysis.
13. Subjects with brain metastases are eligible if they are asymptomatic, are treated or are neurological stable for at least 2 weeks without the use of steroids or on stable or decreasing dose of < 10 mg daily prednisone or equivalent.
14. Subjects must be following an antiretroviral therapy at the moment of the inclusion.

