the possible benefit of this treatment in cancer patients and HIV infection, exploring if activity of durvalumab (MEDI4736) could be higher in cancer that has been produced at least in part due to the chronic immunosuppression. Simultaneously, it will allow us to investigate the effect of disrupting this immunoregulatory pathway might have in reversing cancer pathways and HIV-specific T-cell function during persistent chronic HIV infection in humans.

In this regard, our hypothesis is:

HIV patients with cancer have a similar outcome in terms of tolerability when treated with durvalumab (MEDI4736) monotherapy at the recommended dose than non HIV infected patients.

Objectives:

Primary Objectives:

To explore the feasibility of durvalumab (MEDI4736) monotherapy at the recommended dose of 1500mg every 4 weeks in solid tumors in HIV-1-infected patients.

Secondary Objective(s):

- To assess ORR (RECIST 1.1 and irRECIST) and duration of response.
- To evaluate the PFS rate at 6 months.
- To evaluate the OS rate at 12 months.

[REDACTED]

[REDACTED]

[REDACTED]

[REDACTED]

Study Design:

This is a multicenter, national, nonrandomized, open label trial, phase II trial in subjects with advanced solid tumors and HIV-1 infection. Twenty patients will receive durvalumab.

Patients have to be diagnosed of advanced (metastatic or locally advanced disease without cure options with surgery or radiotherapy) cancer of any of these types: lung cancer, head and neck cancer, cervical cancer, melanoma, anal cancer, pancreatic cancer, gastro-esophageal cancer, triple negative breast cancer, bladder cancer, renal cancer, Cholangiocarcinoma, Kaposi sarcoma, lymphomas, ovarian cancer, Merkel cell carcinoma or any other tumor type in which anti PD-1 or anti PD-L1 antibodies have demonstrated antitumoral activity.

Adverse events (AEs) will be assessed throughout and evaluated using National Cancer Institute (NCI) Common Technology Criteria version of Adverse Events version 4.03 (CTCAE v 4.03).

Tumor measurements by PET-CT, CT scan or MRI will be performed every 8 weeks to determine response to treatment. Response will be evaluated using Response Evaluation Criteria in Solid Tumors version 1.1 (RECIST 1.1) and immune related response criteria (irRECIST).

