17. Known history of active tuberculosis.
18. Any serious or uncontrolled medical disorder or active infection non HIV, that would impair the ability of the subject to receive the treatment of protocol therapy under treating physician criteria.
19. Subjects with previous malignances (except non melanoma skin cancer, and cancer in situ of: bladder, gastric, colon, cervical/dysplasia, melanoma, breast) are excluded unless a complete remission was achieved at least 5 years prior to study entry and no additional therapy is required or anticipated to be required during the study period.
20. Receipt of live attenuated vaccination within 30 days prior to study entry or within 30 days of receiving durvalumab.
21. Female subjects who are pregnant, breast-feeding, male, or female patients of reproductive potential who are not employing an effective method of birth control.
22. Any condition that, in the opinion of the investigator, would interfere with evaluation of study treatment or interpretation of patient safety or study results.
23. Symptomatic or uncontrolled brain metastases requiring concurrent treatment, inclusive of but not limited to surgery, radiation and/or corticosteroids.
24. Subjects with uncontrolled seizures.
25. Patients with tumoral disease in the head and neck region, such as peritracheal or periesophageal lymph node involvement, with infiltration of structures of the digestive, aerea or vascular pathways that represent a risk of increased bleeding.
26. Patients with neuroendocrine tumors of pulmonary origin or pulmonary metastases with evidence of active bleeding.

27. Patients with digestive bleeding.

Investigational Product(s), Dose and Mode of Administration:

Durvalumab, 1500 mg Q4W durvalumab (equivalent to 20 mg/kg Q4W) if > 30 kg.

If patient is ≤ 30 kg, weight-based dosing, equivalent to 20 mg/kg Q4W, should be used (Appendix 2).

Study Assessments and Criteria for Evaluation:

Safety Assessments:

- Safety assessments will be based on adverse event reports, results of clinical laboratory tests, immune safety tests, physical examinations, vital sign measurements, ECOG performance status during the study and up to six months following the last study drug administration. It will be reported based on Common Terminology Criteria for Adverse Events (CTCAE) v4.0.

Efficacy Assessments:

- Tumor response evaluation will be classified according to RECIST 1.1 criteria and irRECIST criteria.

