11. STATISTICAL METHODS AND SAMPLE SIZE DETERMINATION

11.1 Description of analysis sets

The screening analysis set includes all subjects who signed the ICF.

ITT Analysis set: the ITT analysis set will include all subjects who were included into the trials.

Per-protocol analysis set will include all ITT subjects who do not have major protocol violations.

[REDACTED]

[REDACTED]

[REDACTED]

[REDACTED]

[REDACTED]

[REDACTED]

[REDACTED]

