11.2 Methods of statistical analyses

In general descriptive summaries will be presented for the efficacy and safety variables collected. Continuous variables will be summarized using mean, standard deviation, minimum, median, and maximum. Categorical variables will be summarized using frequency counts and percentages.

Unless otherwise specified, the calculation of proportions will be based on the sample size of the population of interest. Count missing observations will be included in the denominator and presented in a separate category.

Clinical Study Protocol

Drug Substance Durvalumab (Medi4736)

Sponsor code: GECP 16/04

Version Number 4.1

Date 14th November 2018

[REDACTED]

Clinical Study Protocol

Drug Substance Durvalumab (Medi4736)

Sponsor code: GECP 16/04

Version Number 4.1

Date 14th November 2018

Clinical Study Protocol

Drug Substance Durvalumab (Medi4736)

Sponsor code: GECP 16/04 [REDACTED]

Version Number 4.1

Date 14th November 2018

[REDACTED]

[REDACTED]

[REDACTED]

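### Does admitting patients without measurable disease, including lymphoma and Kaposi sarcoma, bias the response rate low?

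*Combined protocol and SAP*

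**What the plan says.** Section 2.2 makes response a secondary objective: "To assess ORR (RECIST 1.1 and irRECIST) and duration of response". It gives the purpose of the activity analysis as "in order to determine if activity looks similar to activity reported in solid tumors without HIV- infection".

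The Synopsis, under Efficacy Assessments, states: "Tumor response evaluation will be classified according to RECIST 1.1 criteria and irRECIST criteria". Under Study Design it adds: "Tumor measurements by PET-CT, CT scan or MRI will be performed every 8 weeks to determine response to treatment".

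Section 4.1, criterion 8, lists the eligible cancers, among them "Cholangiocarcinoma, Kaposi sarcoma, lymphomas, ovarian cancer, Merkel cell carcinoma or any other tumor type". None of the 14 inclusion criteria or the 27 exclusion criteria in Section 4.2 mentions measurable disease. Both lists can be read in full.

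On denominators, Section 11.1 says that "the ITT analysis set will include all subjects who were included into the trials". Section 11.2 says, as a default that other text may override, that "the calculation of proportions will be based on the sample size of the population of interest", and then: "Count missing observations will be included in the denominator and presented in a separate category". Section 3.1 describes the planned 20 patients as evaluable, with no readable definition of that word.

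The text after the three analysis sets in Section 11.1, the text after the general paragraphs of Section 11.2, the schedule of assessments and most of Sections 8 and 9 are blacked out.

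**The concern.** The title and the response criteria speak of solid tumours, yet lymphomas and Kaposi sarcoma may enter, and nobody has to have a measurable lesion. Suppose that a patient with no measurable lesion, for example one with Kaposi sarcoma confined to the skin, cannot be scored as a partial responder. If Section 11.2 keeps that patient in the denominator, he or she counts as a non-responder for reasons unrelated to HIV or durvalumab.

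The error would run in one direction only. It would also fall on a figure that the trial means to set beside results in patients without HIV. Section 1.5 cites response rates of 7% to 38% for antibodies of this class in solid tumours. In a trial of 20, each patient is worth 5 percentage points, so a few such patients could make activity in HIV look weaker than it is.

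**Working it through.** **The plan's own figure.** The documents give no planned ORR and no precision for it. The one stated calculation is the Synopsis sample size for the feasibility proportion (50%, 95% confidence, accuracy 22%):

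n = 1.96² × 0.50 × 0.50 / 0.22² = 19.84, rounded up to 20.

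This reproduces the stated 20. The half-width at n = 20 is 1.96 × √(0.25/20) = 21.9 points. ORR plays no part in it.

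**Size of a possible dilution.** Let r be the true response rate among patients who can score a response, and m the number of 20 who cannot. If all 20 are counted, the expected ORR is r × (20 − m)/20. The documents give no m, so 0 to 6 is assumed. The values of r are the two ends of the range in Section 1.5 and an assumed 25%.

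| r | m = 0 | m = 2 | m = 4 | m = 6 |
|---|---|---|---|---|
| 7% | 7.0% | 6.3% | 5.6% | 4.9% |
| 25% | 25.0% | 22.5% | 20.0% | 17.5% |
| 38% | 38.0% | 34.2% | 30.4% | 26.6% |

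The relative loss is m/20, or 10% to 30% for m from 2 to 6. These are upper bounds: the formula gives the m patients no chance of any response, whereas the mechanism concerns partial response only. Any complete response among them reduces the loss.

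**Comparison with sampling error.** Exact (Clopper-Pearson) 95% intervals for 4 responders under different denominators:

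| Denominator | ORR | 95% interval |
|---|---|---|
| 20 | 20.0% | 5.7% to 43.7% |
| 18 | 22.2% | 6.4% to 47.6% |
| 16 | 25.0% | 7.3% to 52.4% |
| 14 | 28.6% | 8.4% to 58.1% |

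At n = 20 the interval is 43.7 − 5.7 = 38.0 points wide. At n = 16 it is 52.4 − 7.3 = 45.1 points wide. Restricting the set moves the estimate by 5 points and widens the interval by about 7. With 20 patients, every count from 0 to 12 responders has an exact interval that overlaps 7% to 38%.

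**Does the text put these patients in the denominator?** Three statements have to be read together.

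- Section 11.2 keeps missing observations in the denominator. A patient who is scanned on schedule but has no target lesion is not plainly a missing observation.
- The same paragraph ties proportions to a population of interest and yields to any more specific rule. No readable text names that population for ORR.
- Section 3.1 plans for evaluable patients.

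The place where an ORR set, a measurability rule or tumour-specific criteria would stand is blacked out. The readable text is therefore compatible with an all-patient ORR and with a response-evaluable ORR.

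**The case for a change.** The best argument for acting is that redaction cannot explain the eligibility lists. They are complete, and they let patients without measurable disease in whatever Section 11 says. The Synopsis is readable where it states how response is classified, and it makes no exception for lymphoma or Kaposi sarcoma. Of the analysis sets that can be read (screening, ITT and per-protocol), none is restricted to patients evaluable for response. A shift smaller than the sampling error is still a one-way error added to it, and a sentence in Section 11 would cost little.

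The facts in that argument stand. The conclusion does not follow from them. Broad entry suits a trial whose primary question is whether patients complete four cycles, and a measurability criterion would bear only on a secondary endpoint. A listed tumour type is not the same as non-measurable disease: the plan provides PET-CT, CT or MRI, and nothing readable shows that patients with lymphoma or Kaposi sarcoma would lack a lesion to follow. No readable passage defines partial response or measurability either, so the mechanism is an assumption here.

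The proposed remedy also has a price. Counting all patients is a recognised conservative choice. Restricting to measurable disease, or taking two tumour types out of the pooled rate, makes a set of 20 smaller and its interval wider. Neither denominator is wrong.

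Nor is the 7% to 38% range a test. Section 1.5 cites it for benefit and risk, and Section 2.2 asks only for an informal impression, noting that mixed tumours and treatment lines are why activity is secondary.

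**Conclusion.** No change is needed. The readable text leaves the ORR denominator and the handling of lymphoma and Kaposi sarcoma unstated, and the missing detail may well be in the redacted parts of Section 11 or of Sections 8 and 9. It does not establish that patients who cannot be scored are counted, and so does not establish a bias.

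If they were counted, the loss would be at most m/20 of the true rate: 0.7 to 2.1 points at 7%, 2.5 to 7.5 points at 25% and 3.8 to 11.4 points at 38%, for an assumed m of 2 to 6. It would be zero if no such patient enrolled. With an interval about 38 points wide at 4 of 20, a shift of that size would seldom alter an informal reading of whether activity looks similar. The primary endpoint and the sample size of 20 are untouched.

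This is a gap that analysts fill sensibly for a descriptive endpoint. Baseline lesion data should come from the planned scans, and the report can show responders over all treated patients and over those with measurable disease, each with an exact interval, without amending the plan.

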4.2 Exclusion criteria

Subjects should not enter the study if any of the following exclusion criteria are fulfilled:

1. Involvement in the planning and/or conduct of the study. Previous enrollment in the present study.
2. Participation in another clinical study with an investigational product during the last 4 weeks.
3. Other untreated coexisting HIV related malignancies.
4. Any previous treatment with a PD1, PD-L1 or PD-L2 inhibitor, including durvalumab.
5. Receipt of the last dose of anti-cancer therapy (chemotherapy, immunotherapy, endocrine therapy, targeted therapy, biologic therapy, tumor embolization, monoclonal antibodies, other investigational agent) 28 days prior to the first dose of study drug.
6. Mean QT interval corrected for heart rate (QTc) ≥ 470 ms calculated from 3 electrocardiograms (ECGs) using Fridericia's Correction.

7. Current or prior use of immunosuppressive medication within 28 days before the first dose of durvalumab, with the exceptions of intranasal and inhaled corticosteroids or systemic corticosteroids at physiological doses, which are not to exceed 10 mg/day of prednisone, or an equivalent corticosteroid.
8. Any unresolved toxicity (CTCAE grade 2) from previous anti-cancer therapy. Subjects with irreversible toxicity that is not reasonably expected to be exacerbated by the investigational product may be included (e.g., hearing loss, peripherally neuropathy).
9. Any prior Grade ≥ 3 immune-related adverse event (irAE) while receiving any previous immunotherapy agent, or any unresolved irAE >Grade 1.
10. Active or prior documented autoimmune disease within the past 2 years
NOTE: Subjects with vitiligo, Grave's disease, or psoriasis not requiring systemic treatment (within the past 2 years) are not excluded.
11. Any syndrome that requires systemic corticosteroid/immunosuppressive medications EXCEPT for syndromes which would not be expected to recur in the absence of an external trigger (vitiligo, autoimmune thyroiditis, or type 1 diabetes mellitus are permitted to enroll).
12. Active or prior documented inflammatory bowel disease (e.g., Crohn's disease, ulcerative colitis).
13. History of primary immunodeficiency.
14. History of allogeneic organ transplant.
15. History of hypersensitivity to durvalumab or any excipient.
16. Uncontrolled intercurrent illness including, but not limited to, ongoing or active infection, symptomatic congestive heart failure, uncontrolled hypertension, unstable angina pectoris, cardiac arrhythmia, active peptic ulcer disease or gastritis, active bleeding diatheses including any subject known to have evidence of acute or chronic hepatitis B or C, or psychiatric illness/social situations that would limit compliance with study requirements or compromise the ability of the subject to give written informed consent.
17. Known history of active tuberculosis.

18. Any serious or uncontrolled medical disorder or active infection non HIV, that would impair the ability of the subject to receive the treatment of protocol therapy under treating physician criteria.
19. Subjects with previous malignances (except non melanoma skin cancer, and cancer in situ of: bladder, gastric, colon, cervical/dysplasia, melanoma, breast) are excluded unless a complete remission was achieved at least 5 years prior to study entry and no additional therapy is required or anticipated to be required during the study period.
20. Receipt of live attenuated vaccination within 30 days prior to study entry or within 30 days of receiving durvalumab.
21. Female subjects who are pregnant, breast-feeding or male or female patients of reproductive potential who are not employing an effective method of birth control.
22. Any condition that, in the opinion of the investigator, would interfere with evaluation of study treatment or interpretation of patient safety or study results.
23. Symptomatic or uncontrolled brain metastases requiring concurrent treatment, inclusive of but not limited to surgery, radiation and/or corticosteroids.
24. Subjects with uncontrolled seizures.
25. Patients with tumoral disease in the head and neck region, such as peritracheal or periesophageal lymph node involvement, with infiltration of structures of the digestive, aerea or vascular pathways that represent a risk of increased bleeding.
26. Patients with neuroendocrine tumors of pulmonary origin or pulmonary metastases with evidence of active bleeding.
27. Patients with digestive bleeding.

